6.5.4 Secondary safety outcome analysis: Incidence of infusion reactions

Research Questions:	Data Variables:	Data Source:

Do we find any infusion reactions during receipt of infusion and during the infusion follow-up period?
 
Do infusion reactions vary from demographic characteristics or comorbidities?
	
 • Date of infusion treatment • Date of infusion reactions of interest • Demographics • Elixhauser conditions 	
 • Patient self-reported data • Optum infusion nurse data • UHC claims data

Clinicians will start with qualitative analysis on a case by case basis. We will report descriptive statistics according to the data we will obtain. If we have a sufficient size of study participants with particular infusion reactions, we can calculate descriptive statistics, run Chi-square independence test and Kruskal-Wallis test to examine if infusion reactions vary from demographics or comorbidities.

6.5.5 Secondary safety outcome analysis: Adverse events

Research Questions:	Data Variables:	Data Source:

Do we find any self-reported adverse events between receipt of infusion and day 28 from study participants?
 
Do patient-reported adverse events vary from demographic characteristics or comorbidities?
	
 • Date of infusion treatment • Date of infusion reactions of interest • Demographics • Elixhauser conditions 	
 • Patient self-reported data • Optum infusion nurse data • UHC claims data

Once adverse events are defined or classified and adjudicated, we can perform the same methodology described in 6.5.4.

6.5.6 Subgroup Analysis

Research Questions:	Data Variables:	Data Source:

Is the time gap between a COVID positive test result and an infusion associated with COVID hospitalization?
 
Do we find any patterns in a subgroup with certain demographic characteristics or comorbidities of interest?
	
 • Flag of infusion treatment • Demographics • Elixhauser conditions • Symptoms 	
 • Patient self-reported data • Optum infusion nurse data • UHC claims data • CDSM COVID labs data • ProtectWell data

There are two pre-specified subgroup analyses we will pursue aside from the primary and secondary objectives (efficacy and safety) above.

First, we want to understand if the timing of the infusion relative to a positive COVID test, impacts hospitalizations. We will compute the Cramer's V and phi coefficient as one-number summary of correlation between two categorical variables when we group time gap between date of COVID positive and date of home infusion. If considering this time gap as a continuous variable, we will run a simple logistic regression model to examine if time gap is associated with the hospitalization rate at Day 28. Then, we will apply the same methodology described above for categorical and continuous covariates and binary outcomes.

Second, we want to understand if the timing of the infusion relative to a symptom onset, impacts hospitalizations. We will compute the Cramer's V and phi coefficient as one-number summary of correlation between two categorical variables when we group time gap between date of COVID positive and date of home infusion. If considering this time gap as a continuous variable, we will run a simple logistic regression model to examine if time gap is associated with the hospitalization rate at Day 28. Then, we will apply the same methodology described above for categorical and continuous covariates and binary outcomes.

7. RISKS AND BENEFITS

7.1 Risks and Risk Mitigation

Bamlanivimab (LY3819253) is an investigational product for those who are at high-risk of experiencing more severe symptoms if they contract COVID-19. The receipt of Bamlanivimab (LY3819253) occurs under an Optum Infusion Nurse monitored procedure, with appropriate protections in place to address any expected infusion reactions (either from Bamlanivimab (LY3819253) or the process of infusion) as well as to address any unexpected events that occur either pre, during or post-infusion of Bamlanivimab (LY3819253). Nurses will remain for a period of up to two hours while preparing for, during and follow-up after infusion to confirm that the participant is stable and does not require any further medical oversight.

Participants will self-report a baseline on Day 1 after receipt of the infusion and this baseline will create the landscape for their wellness reports Day 2 through 28 after receipt of infusion. We will have additional contacts for participants external to the daily ProtectWell wellness check via the app, including using post-infusion Optum Infusion clinical support features as needed for anyone who is experiencing anything that requires more immediate attention.

The risk of loss of confidentiality given the number of partners engaging to execute the research is always a possibility. The risk is mitigated by using appropriate protected electronic files and to avoid exchanging information that contains protected health information (PHI) and no PHI will be released to the external partners, but personal identifying information (i.e. name, address) will be provided as needed.

7.2 Benefits

There is no guarantee of direct benefit from participating. The study will test the hypothesis that treatment with Bamlanivimab (LY3819253) will reduce the incidence of COVID-19 related hospitalization and mortality in mild or moderate COVID-19 patients who are at high risk of progressing to severe COVID-19 and/or hospitalization, relative to matched external controls. The study will further describe the incidence of infusion related reactions and patient reported adverse events in patients treated with Bamlanivimab (LY3819253).

Given the available data and the recent emergency use authorization of Bamlanivimab (LY3819253) in this patient population, the benefit-risk assessment for this study is favorable.

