2. STUDY PURPOSE & OBJECTIVES

The purpose of this study is to: Assess the safety of at-home infusion of Bamlanivimab and to determine whether symptomatic high risk COVID-19 participants will have a reduction in hospitalizations compared to a real-world external control population when provided with a combination of symptom tracking and single dose administration of Bamlanivimab (LY3819253) via an at-home infusion visit.

The primary objectives are:

Safety

- To describe the incidence of infusion reactions during receipt of infusion and during the defined infusion follow-up period
- To describe the incidence of patient reported adverse event outcomes through Day 28

Efficacy

- To determine the incidence of COVID-related hospitalization at Day 28 among Bamlanivimab-treated participants (**long-term** – hospitalization rate via medical records/claims data and **short-term** via participant self-report during active study participation) relative to external controls.

The exploratory objective is:

- To determine the incidence of COVID-related mortality at Day 28 among Bamlanivimab-treated patients relative to external controls.

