- Grouping:

- 1-3 rating (potential flag for clinical outreach)
 - 4-7 rating (feeling OK – no action needed)
 - 8-10 (feeling good/great – no action needed)
- Day 1 rating dictates baseline for Days 2-28
 - Goal is for patients to either stay steady at Day 1 rating or to continue to see an increase as they progressively feel better
- Rating drops between Day 2 and Day 28
 - If rating drops back to a 4 or above from where the patient was (for example – registered a 6 and the next day registered a 4) – no clinical follow-up at that time but will get a note recognizing that they took a step back in their ratings
 - If rating drops back to 3 or below from where the patient was (for example – registered a 5 and the next day registered a 3) – this would trigger clinical outreach by the UHG Clinical Team
- Post-Infusion Day 1 – Baseline
 - It is fine to start at a 1-3 (and likely expected as these folks have COVID-19 and even though symptoms are mild to moderate – they are probably not feeling too well)
 - It is fine to stay in the 1-3 range for a few days if they are either:
 - Staying the same as baseline
 - Seeing minor increases (for example – going from a 1 to a 2 or a 2 to a 3)
 - If the patient continues to check the same rating but does not get above a 3 – this would be flagged for clinical follow-up – the clinical lead will assess what day of the experience the participant is in and either flag them for clinical follow-up connection or document permitting another wellness day check-in to see if the level of wellness improves
- Clinical Follow-up/Outreach During 28-day active period
 - UHG R&D internal clinical team (leadership role is a RN) will review the twice daily reports that have extracted any participants who have a 1-3 rating
 - This report will dictate who requires clinical follow-up/outreach or it will be documented as to the reason why clinical connection was not (see example above – closer to day 1 post-infusion)
 - Clinical follow-up will occur with consistency by using the “Symptoms List for Clinical Outreach and Action Plan”
 - Information collected during clinical follow-up will be consistently documented in the participant file and reports for symptoms and other issues being reported will be generated for assessment as needed (i.e. aggregate reports for assessing severity/frequency of events as needed)
 - Clinical action taken in response to reported symptoms/issues will also be documented
- Overall goal

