3.1 Primary Objective

The primary objective is related to efficacy and is:

- To determine the incidence of COVID-related hospitalization at Day 28 among Bamlanivimab-treated relative to external controls.

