4.3 Sample Size Determination

[figure not shown]
To evaluate treatment effects based on the discrete clinical endpoint (hospitalization rate at Day 28 post infusion), we compared the proportion of events (i.e., prevalence rate or COVID hospitalization rate) between treatment and matched-control group which is our primary objective of interest. Specifically, we are interested in testing the efficacy (superiority) of treatment effects, which can be written formally in one- or two-sided hypotheses. Assume the null hypothesis is two-sided. We performed the power analyses based on a 5% level of significance (Type-I error) for a set of values of power (i.e., 0.75, 0.80, 0.85, 0.90, 0.95). We obtained the minimally required sample size for multiple scenarios - (a) hospitalization rate (0.20, 0.25, 0.30, 0.35) based on BCRT and CDSM data (b) different possible efficacy rates (reduction rates in hospitalization after using treatment). We used multiple methods - (i) a two-sample proportion test in detecting a difference between two binomial probabilities (Casagrande, 1978) (Fleiss, 1980) and (ii) McNemar's test (Agresti, 2003).

The former test statistic follows Gaussian distribution asymptotically exploiting large sample theory and the latter is designed to test categorical shift (or association) in responses (hospitalization rate in our example) between treatment and control group where the idea is to cast the data into a 2 x 2 contingency table. While both these methods provide competitive and comparable results, reported below are the results based on the first method, a two-sample proportion test with continuity correction. The one-sided hypothesis requires a smaller sample size than that of a two-sided test.

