Figure 1 illustrates the sample size required with a case and control ratio being 1:1 for different hypothetical scenarios. As expected, when the true prevalence rates between treatment and control groups are small, it requires a larger sample size to detect a statistically significant difference. As reported in the Lilly SARS-CoV-2 Neutralizing Antibody Program Update, the hospitalization rate for the treatment (i.e., LY-CoV555 Mono) group drops by 75% compared to that of the placebo group. Based on this relative change, we will need a total sample size less than 1,000; follow the power curves (i.e., corresponding to 0.10 Type-II error) in Figure 1 top-right panel with 75% (approximately) reduction rate. For example, using the COVID hospitalization rate of 25%, reported below in Table 2, are the minimum COVID diagnosed patients required to detect varying differences between the proportions at a 5% level of significance with 90% power of rejecting a two-sided null hypothesis.

Table 2. A case study for baseline hospitalization rate of 25%.

Absolute differences (assumed) between prevalence rates of treatment and control group (% reduction from baseline rate)	Total sample size (treatment and control as 1:1)
0.24 (95%)	97
0.21 (85%)	129
0.19 (75%)	175
0.16 (65%)	244
0.14 (55%)	355
0.11 (45%)	550
0.09 (35%)	940
0.06 (25%)	1,899
0.04 (15%)	5,416
0.01 (5%)	49,900

[figure not shown]

Figure 1. Power analyses at 5% level of significance for six scenarios with baseline COVID hospitalization rates of 15% (top-left), 20% (top-right), 25% (middle-left), 30% (middle-right), 35% (bottom-left), and 40% (bottom-right) based on CDSM and BCRT databases. Varying prevalence rates along with reduction (in parenthesis) in hospitalization from baseline (i.e., control group) for the treatment group are considered (X-axis) as 95% to 5%. Reference lines corresponding to 5,000 and 2,000 sample size are drawn for convenience of comparison.

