5.1 General Considerations

Statistical analysis of this study will be the responsibility of the sponsor or its designee. All tables, figures, and listings will be created using the data described in Table 1 and Section 4.7 (unless otherwise noted), including data during study participation. While not reflected in a table, figure, or listing, any data collected after study participation (e.g., in the Lilly Safety System or collected through queries to the investigator) may be discussed in a clinical study report (CSR) or integrated summary document when deemed relevant. Unless otherwise noted, displays will include columns for study participants and controls will be displayed.

Not all displays described in this statistical analysis plan (SAP) will necessarily be included in the CSR. Not all displays will necessarily be created as a “static” display. Some may be incorporated into interactive display tools instead of, or in addition to, a static display. Any display described in this SAP and not provided would be available upon request.

Treatment differences will be evaluated based on a two-sided significance level of 0.05 for all efficacy analyses. Ninety-five percent confidence intervals for the estimated event rate, odds ratio/hazard ratio will be provided. While we describe many methods addressing different uncertainties, we may not need to perform all analyses mentioned in the draft. Additional exploratory analyses of the data will be conducted as deemed appropriate. All statistical analyses will be performed using R 3.6 (or a higher version).

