5.8.2 Sensitivity Analyses

The validity of all the above analyses relies on the assumption of 'no unmeasured confounding'. That is, the identification of average treatment effects in observational studies is achieved by assuming that the correct set of confounders has been measured and properly included in the relevant models. Thus, sensitivity analysis for the potential impact of unmeasured confounding is important as the assumption of no unmeasured confounding cannot be completely verified. In this study, potential unmeasured confounders include the frequency of interaction with clinicians (e.g., doctors or nurses), viral load (e.g., cycle threshold value from polymerase chain reaction tests), COVID-19 variants (e.g., B.1.1.7 and B.1.351 first identified in the United Kingdom and South Africa, respectively), lifestyle patterns (e.g., activity level or diet pattern), psychosocial factors (e.g., a patient's psychological reaction when facing COVID-19 and its interaction with the disease progression, or if a patient has the support network such as family and friends), etc.

Assuming it is not possible to obtain information on specific unmeasured confounders, plausibility/one-number summary methods, such as the E-value, may be performed as an initial assessment of the robustness of the primary analysis findings to the potential for unmeasured confounding. Specifically, the E-value (VanderWeele, 2017) and the proportion of unmeasured confounding (Bonvini, 2020) may be used to evaluate the robustness of the primary objective in our study (i.e., the difference in COVID-19 hospitalization during Days 1 to 28 analysis between matched study participants and matched controls).

The E-value is defined as "the minimum strength of association, on the risk ratio scale, that an unmeasured confounder would need to have with both the treatment and the outcome to fully explain away a specific treatment-outcome association, conditional on the measured covariates." E-values can be based on the adjusted treatment effect estimate or the confidence limit endpoint of interest.

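### The stated purpose is tracking combined with the drug, but the hypothesis credits bamlanivimab alone; the design can support only a claim about the home programme against record-based controls

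*Protocol*

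**What the plan says.** The purpose in Protocol 2 is to learn whether high-risk symptomatic participants have fewer hospitalizations than external controls "when provided with a combination of symptom tracking and single dose administration of Bamlanivimab" at a home infusion visit. SAP 3 repeats this purpose.

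The hypothesis in Protocol 7.2 drops the tracking: "The study will test the hypothesis that treatment with Bamlanivimab (LY3819253) will reduce the incidence of COVID-19 related hospitalization and mortality". SAP 3.1 gives the primary objective as "To determine the incidence of COVID-related hospitalization at Day 28 among Bamlanivimab-treated relative to external controls", and the efficacy objective in Protocol 2 is framed the same way. The sizing text (Protocol 8.2, SAP 4.3) takes its 75% reduction from a comparison of the drug with placebo.

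What participants receive is spread over several sections:

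- Protocol 5.7 (Enrollment / Consent Plan): daily app tracking, a test when symptoms are reported, the infusion, and wellness checks to Day 28.
- Protocol 7.1: a nurse present for up to two hours.
- Protocol 9.1: a report of feeling worse triggers a phone call, which may end in advice to seek care.
- Protocol Appendix 3: a clinical team "will review the twice daily reports that have extracted any participants who have a 1-3 rating".

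SAP 4.2 says the controls are not enrolled. They are identified from records and given a synthetic treatment date (SAP 4.5). No tracking, home visit or outreach is described for them.

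On robustness, SAP 5.8.2 says "potential unmeasured confounders include the frequency of interaction with clinicians (e.g., doctors or nurses") along with viral load, variants, lifestyle and psychosocial factors. It then offers the E-value as an optional first assessment.

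**The concern.** The documents name two different contrasts. One is a programme that includes the drug; the other is the drug. The design can estimate only the first, because the participants' extra services start and stop with study participation.

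Those services bear on the endpoint. An outreach call may keep a participant at home through early advice, or may send that participant to care and so to an admission. A reduction could therefore belong partly to the monitoring, and a null result could hide a drug effect offset by closer surveillance. Neither document limits its conclusion to the programme, and no planned analysis isolates the drug. A reader of the final report would take the odds ratio or hazard ratio as an effect of bamlanivimab.

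**Working it through.** **1. The plan's own figures.** The inputs are from SAP 4.3 and 5.1: "at a 5% level of significance with 90% power of rejecting a two-sided null hypothesis"; "reported below are the results based on the first method, a two-sample proportion test with continuity correction"; "Treatment differences will be evaluated based on a two-sided significance level of 0.05 for all efficacy analyses". For the 75% row of Table 2, p1 = 0.25, p2 = 0.0625, d = 0.1875 and the mean proportion is 0.15625.

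- Uncorrected n per group = [1.960·√(2·0.15625·0.84375) + 1.282·√(0.25·0.75 + 0.0625·0.9375)]² / 0.1875² = 76.7.
- Corrected n = (n/4)·[1 + √(1 + 4/(n·d))]² = 87.05, a total of 174.1. Rounded up this is 175, as stated.

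The other nine rows also reproduce. For the SAP 4.4.2 scenario (15% to 10%, power 0.8), 686 per group are needed, or 726 with the correction. At 1,000 per group power is about 0.92 (0.91 corrected). The sizing is sound; the question is what the estimated difference represents.

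**2. Which components are one-sided.**

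| Component | Participants | Controls |
|---|---|---|
| Daily app tracking and wellness ratings | Yes; contact details instead if the app cannot be used (Protocol 6.1) | Not described |
| Home nurse visit | Yes, with the infusion | Not described |
| Triggered outreach | Only on low or worsening ratings | Not described |
| SARS-CoV-2 test | Yes | Yes, a confirmed positive is required |
| Some clinician contact | Yes | Yes: care sought at a facility (Protocol 5.3) or symptoms in the medical record (SAP 4.4.1) |

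The first three rows come with study entry or follow the index date. Matching on 2019 comorbidities, demographics and prior treatment cannot balance them.

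**3. What the services alone could produce.** Assume no drug effect, a control rate of 15%, and a reduction due only to the services. The test is two-sided at 5%, treated as unpaired.

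| Assumed reduction from services | P(significant, favouring treatment), 1,000 per group | 7,500 per group |
|---|---|---|
| 10% | 0.16 | 0.75 |
| 20% | 0.50 | >0.99 |
| 25% | 0.70 | >0.99 |

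The opposite direction matters as well. If the drug had a risk ratio of 0.667 and the services raised admissions by 20% (assumed, multiplicative), the observed ratio would be 0.667 × 1.2 = 0.80. Power at 1,000 per group would fall from 0.92 to 0.50.

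**4. The E-value beside the one-sided limit.** A factor associated with treatment by RR_EU and with outcome by RR_UD can bias the risk ratio by at most

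B = RR_EU·RR_UD / (RR_EU + RR_UD − 1).

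Setting the two associations equal and B = 1/RR gives the E-value, 1/RR + √[(1/RR)(1/RR − 1)]. As RR_EU grows without limit (a factor in all treated and no controls), B tends to RR_UD, so the required outcome association is 1/RR.

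| Assumed observed RR | E-value | 1/RR |
|---|---|---|
| 0.67 (15% to 10%) | 1.50 + √(1.50·0.50) = 2.37 | 1.50 |
| 0.50 | 2 + √2 = 3.41 | 2.00 |
| 0.25 | 4 + √12 = 7.46 | 4.00 |

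For the confidence limit at 100/1,000 against 150/1,000, SE(log RR) = √(0.90/100 + 0.85/150) = 0.121, so the 95% interval is 0.53 to 0.85. The upper limit (0.845 unrounded) has an E-value of 1.65 and 1/RR of 1.18, about a 15% reduction.

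**The case against.** Both purpose statements already name the combination. SAP 3.1 compares incidence in a labelled group and does not itself claim sole attribution, and the drug-only hypothesis stands in a section on benefits. This is fair, and it makes the defect one of inconsistency. It does not remove it: the hypothesis credits the drug, and nothing tells a reader that the result belongs to the programme.

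A reader might go further and infer that the E-value plan treats the whole programme as an ordinary confounder and so conceals the problem. The documents do not support that:

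- SAP 5.8.2 lists only clinician contact. Tracking, home testing and monitored follow-up are not on the list, and the entry can mean ordinary healthcare contact, which is a legitimate confounder.
- The E-value is optional. Table A10 places it beside the proportion of unmeasured confounding, and the text mentions negative controls and other methods.
- The E-value sets no limit on either association. The 1/RR figure is the limiting case of the same bound, so the method is not wrong.
- Clinician contact and testing are not absent in controls, and outreach reaches only some participants. For triggered calls the effect among those called would have to exceed 1/RR. The limit is closest for the nurse visit and daily monitoring.

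A reader might also infer that the E-value necessarily overstates robustness. For a protective estimate it does so only if the services lower admissions. If they raise them, the estimate is biased towards the null. Nor do the documents describe the controls' care, so calling the comparator usual care would go beyond them.

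**Conclusion.** The point holds as a mismatch between the stated purpose and the hypothesis and objective, together with an unstated limit on attribution. The primary comparison estimates the effect of the home programme, including the drug, against record-based controls. Neither a positive nor a negative result can be assigned to bamlanivimab alone.

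The documents give no effect for the monitoring, so its size and sign are unknown. The rejection probabilities rest on assumed reductions of 10% to 25%, a 15% control rate and an unpaired approximation. The 1/RR values are minimums for a component present in every participant and no control, and they matter if the services lower admissions. The planned sample sizes, the matching and the choice of the E-value are not shown to be wrong by this point.

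**What to change.** 1. In Protocol 2 and 7.2 and SAP 3.1 and 5.8, define the contrast as the home programme (tracking, testing, infusion visit and monitored follow-up) versus record-based external controls. State that the difference cannot be attributed to bamlanivimab alone.
2. In SAP 5.8.2, keep clinician contact in the list of potential confounders, and add that monitoring delivered by the study is part of the intervention.
3. If the E-value is reported, add 1/RR beside it in Table A10. Label it as the outcome association that a factor present in all treated and no controls would need, relevant if the programme's other components lower admissions.

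The cost is wording in both documents, one table entry and a narrower claim. No data collection, sample size or participant care changes.
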